### **Dosage Modification due to Drug Interactions**

Strong CYP1A2 Inhibitors (e.g., fluvoxamine, enoxacin): Reduce Pirfenidone to 267 mg three times a day (801 mg/day).

Moderate CYP1A2 Inhibitors (e.g., ciprofloxacin) With use of ciprofloxacin at a dosage of 750 mg twice daily, patients will reduce Pirfenidone to 534 mg three times a day (1602 mg/day).

## **WITHDRAWAL**

### **Discontinuation of Patients:**

The investigator will discontinue patients from the study drug or the study or both in the following circumstances:

- The patient, for any reason, requires treatment with another therapeutic agent that has been demonstrated to be effective for treatment of the study indication. In this case, discontinuation from the study occurs prior to introduction of the new agent.

- The investigator decides that the patient should be withdrawn from the study. If a serious adverse event or a clinically significant laboratory value is the basis for this decision, the investigator will discontinue the study therapy and take appropriate measures. The investigator must **immediately** notify the study sponsor or its designee.
- The patient or attending physician requests withdrawal of the patient from the study.
- The investigator or the study sponsor stops the study or stops the patient's participation in the study for medical, safety, regulatory, or other reasons consistent with applicable laws, regulations, and good clinical practice (GCP).
- The study therapies have shown unacceptable toxicity.
- The patient becomes pregnant or fails to use adequate birth control (for women with reproductive potential).
- The patient is noncompliant with study procedures.

When a subject withdraws before completing the study, the reason for withdrawal is to be documented in the CRF and in the source document.

Study agents assigned to the withdrawn subject may not be assigned to another subject. Subjects who withdraw will not be replaced.

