## 5 SUBJECT SELECTION

### 5.1 Study Population

Subjects with a diagnosis of RCLAD who meet the inclusion and exclusion criteria will be eligible for participation in this study.

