### 5.2 Inclusion Criteria

1. Subjects aged 18 to 80 years old who underwent bilateral lung transplantation at UCSF.
2. Diagnosis of RCLAD based on the International Heart and Lung Transplant (ISHLT) classification. The diagnosis of RCLAD is based on spirometry (FEV1 ≤ 80% and FVC ≤ 80% of best post-transplant baseline) and CT scan (e.g. pleuroparenchymal fibroelastosis) findings.
3. Subjects with steady-state blood concentration of tacrolimus, as assessed by 10-12 hour trough level.

[figure not shown]

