### 5.3 Exclusion Criteria

Patients with RCLAD will be excluded if they are, in the judgment of the investigator, unlikely to tolerate pirfenidone. Other exclusion criteria will include:

1. FVC decline related to non-RCLAD causes (e.g. pulmonary edema, pleural effusion, etc).
2. Patients with any severe comorbidity complicating RCLAD which might determine their prognosis and functional level (e.g. active malignant disease) within the last 12 months.
3. Patients who have resumed smoking after transplantation.
4. Renal insufficiency (creatinine clearance < 30 ml/min calculated by the CKD-Epi formula).
5. Total bilirubin above the upper limit of the normal range (ULN)
6. Aspartate or alanine aminotransferase (AST or ALT) > 3 times the ULN.
7. Known allergy of hypersensitivity to Pirfenidone
8. Ongoing use or expected use of any of the following therapies:
  - Strong inhibitors of CYP1A2 (e.g. fluvoxamine or enoxacin).
  - Moderate inhibitors of CYP1A2 (e. g. mexiletine, thiabendazole, or phenylpropanolamine). Ciprofloxacin will be allowed only at doses equal or less than 500 mg BID.
9. Inability to provide informed consent.

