## **DOSE MODIFICATIONS**

### **Dose-reduction Procedure for Adverse Event Management:**

If patients experience significant adverse reactions (i.e., gastrointestinal, photosensitivity reaction or rash), they will have the following temporary dose reduction: reduce dose to 267 mg three times daily (801 mg/day) for 14 days, followed by 534 mg three times daily (1602 mg/day) for another 14 days, prior to returning to the protocol dose of 801 mg three times daily (2403 mg/day). If adverse reactions do not resolve with reducing dose to 267 mg three times daily (801 mg/day) for 14 days, patients will discontinue pirfenidone for 14 days. Any return to protocol dose level after dose reduction must follow documentation of resolution of the adverse event and after discussion with the medical monitor.

If a patient exhibits 2-3 times the upper limit of normal (ULN) ALT and/or AST elevation without symptoms or hyperbilirubinemia after starting Pirfenidone therapy, he/she will discontinue Pirfenidone for 14 days and reinitiate treatment by undergoing the initial 4-week titration regimen up to the full maintenance dosage if tolerated and repeat liver chemistry tests are within normal limits. We will exclude other causes, monitor the patient closely, and repeat liver chemistry tests as clinically indicated.

If a patient exhibits >3 times ULN ALT and/or AST elevation he/she will permanently discontinue Pirfenidone and will not be re-challenged with it.

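### Pregnancy and inadequate birth control are grounds for stopping, but no entry criterion, screening step or scheduled test addresses either before the first dose

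*Combined protocol and SAP*

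**What the plan says.** The stopping rule is in the Withdrawal part, under Discontinuation of Patients. Its opening is mandatory: "The investigator will discontinue patients from the study drug or the study or both in the following circumstances". One of the listed circumstances is "The patient becomes pregnant or fails to use adequate birth control (for women with reproductive potential".

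Eligibility is defined in 5.1 by the listed criteria and nothing else: "Subjects with a diagnosis of RCLAD who meet the inclusion and exclusion criteria will be eligible for participation in this study". The first inclusion criterion in 5.2 is open to both sexes and covers reproductive age: "Subjects aged 18 to 80 years old who underwent bilateral lung transplantation at UCSF". The other two concern the RCLAD diagnosis and a steady tacrolimus level. Section 5.3 opens with one discretionary exclusion, "Patients with RCLAD will be excluded if they are, in the judgment of the investigator, unlikely to tolerate pirfenidone", followed by nine numbered items. The synopsis repeats the same topics.

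Pregnancy appears elsewhere only in the safety-reporting text: 11.3.2.6 (Pregnancy), 11.3.2.7 (Post-Study Adverse Events), the reporting timelines, the paragraph on female partners of male patients, and the special situation reports.

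**The concern.** The plan regards pregnancy, or lack of adequate birth control in a woman who could become pregnant, as serious enough to require stopping. A condition of that kind can usually be applied before treatment starts, which prevents exposure; a stopping rule only reacts once exposure has begun. Here the condition stands only on the stopping side.

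At stake is the safety of a woman, and of a pregnancy, exposed to study drug when a simple check would have prevented it. Consistency is also at stake: staff who follow section 5 to the letter may enrol and dose someone to whom the Withdrawal section could then apply.

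**Working it through.** No arithmetic is involved and there is no planned figure to reproduce. The check is to read every place where an entry condition or pre-dose test could stand, and set it beside the stopping rule.

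| Place in the document | What it covers | Items on pregnancy or birth control |
|---|---|---|
| 5.2 and synopsis, inclusion | Age and bilateral transplant; RCLAD diagnosis; steady tacrolimus level | 0 of 3 |
| 5.3 and synopsis, numbered exclusions | Other causes of FVC decline; severe comorbidity; smoking; renal function; bilirubin; AST/ALT; allergy; CYP1A2 inhibitors; inability to consent | 0 of 9 |
| 5.3, opening sentence | Investigator's judgment of likely tolerance of pirfenidone | Not mentioned |
| 4.1, screening steps | Spirometry algorithm or referral; CT review; pharmacist's check of tacrolimus stability | 0 of 3 |
| Section 6, Schedule of Events | Start drug; coordinator call; tacrolimus; liver tests; clinic visit; FVC; CT; stop drug | 0 of 8 rows |
| 11.3.2.6, 11.3.2.7, reporting timelines, special situations | Reporting a pregnancy or exposure that has occurred | Reporting only |
| Withdrawal | Mandatory discontinuation | Both named |

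Total on the entry side: 0 of 3 + 9 = 12 numbered criteria.

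Two cases follow.

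1. *A woman who could become pregnant and uses no birth control.* She can satisfy all 12 criteria and the three screening steps, and 5.1 then makes her eligible. If nothing changes once she is on study, the birth-control ground under Withdrawal applies to her.

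2. *A woman with an undetected pregnancy.* No criterion asks about pregnancy and no test looks for it. The first column of the schedule is week 1, when pirfenidone starts. Liver and renal limits are entry criteria, so baseline values for those must be obtained even without a screening column. With no pregnancy criterion, nothing implies a pregnancy check. The stopping ground also speaks of *becoming* pregnant, which taken strictly describes a new pregnancy, not one present at entry.

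The extension inherits the gap: the Protocol Amendment text in section 6 requires subjects to go on meeting the original criteria.

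**The case against.** The strongest reply is that the two sets of rules do not formally contradict each other. The Withdrawal list describes events during participation, and failing to use birth control can be read in the same way. A woman using none at screening could start before or after enrolment. This stands: the defect is an omission, and a reader should not infer that every such woman has to be stopped the moment she enrols. It does not supply the missing entry condition or the missing check.

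Three stronger inferences are tempting and should not be drawn.

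- *That the plan normally aligns entry and stopping limits, so this is an anomaly.* The liver limit suggests it: 5.3 excludes "Aspartate or alanine aminotransferase (AST or ALT) > 3 times the ULN", and Dose Modifications says "If a patient exhibits >3 times ULN ALT and/or AST elevation he/she will permanently discontinue Pirfenidone and will not be re-challenged with it". But a value of 2 to 3 times ULN is allowed at entry and brings a 14-day stop on treatment, while CYP1A2 inhibitors are excluded at entry and met by dose reduction later. Other stopping grounds, such as noncompliance, also have no entry counterpart. The case cannot rest on this parallel.
- *That a woman stopped on this ground costs the trial one of its 10 places and erodes the margin over the 8 subjects said to be required.* The plan does say "Subjects who withdraw will not be replaced". But it also allows stopping the drug alone, and tacrolimus is measured weekly for the first 6 weeks, so a woman stopped after some weeks may still supply an on/off pair. The loss does not follow.
- *That a known pregnancy would have to continue on drug, or that women receive no contraceptive advice.* The other Withdrawal grounds (investigator's decision; medical or safety reasons) permit stopping once a pregnancy is known. The consent pages are not available for review, and the form may cover contraception for women. Consent advice could narrow the birth-control gap in practice, but it would be neither an entry criterion nor a test.

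**Conclusion.** The point holds as a gap in patient safety and consistency. The plan makes pregnancy and inadequate birth control grounds for mandatory discontinuation, yet has no pregnancy exclusion, birth-control requirement or pre-dose check in the synopsis, 4.1, 5.2, 5.3 or the Schedule of Events. As written, a woman using no birth control is eligible, and an undetected pregnancy would not be found before the first dose.

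The number affected is unknown and may be zero: the documents do not say how many of the 10 subjects will be women who could become pregnant. They also give no size for any fetal risk, and none is assumed. No effect on sample size, power or the tacrolimus comparison is claimed. The conclusion rests on the visible criteria in section 5 and the synopsis being complete, which their numbering supports. The change should be made because the plan already accepts the condition as a reason to stop, and applying it earlier is cheap.

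**What to change.** - In 5.2/5.3 and the synopsis, exclude women who are pregnant. Require women who could become pregnant to use adequate birth control, with accepted methods named, from the first dose to 28 days after the last dose. That matches the reporting window in 11.3.2.6.
- Confirm pregnancy status before the first dose, and show this check in the Schedule of Events.
- Under Discontinuation of Patients, change the wording to *is or becomes pregnant*.

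The cost is a protocol amendment, which needs prior written IRB approval under 10.1, and one routine test for each woman concerned. Because patients use their own chosen laboratories for monitoring, the test may need a separate order. The consent form may need a line, and a rare candidate may be excluded. Endpoints and analyses do not change.
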